#### **11.10.2.2.1 Hematological Adverse Events of Special Interest Confirmatory Monitoring**

When an event is identified as meeting the pre-specified criteria for decrease from baseline in a laboratory sample at a post-randomization visit (sample 1) and confirmed in a second consecutively drawn sample (sample 2), the following additional monitoring will be put into place. Confirmation is defined as a repeat value that 1) meets the magnitude of decrease criterion from baseline relative to sample 1 and 2) that does not show a meaningful increase relative to sample 1. Baseline for this purpose is defined as the lowest of the available pre-randomization values.

If the decrease is confirmed, additional weekly samples for the ensuing 2 weeks (sample 3 and sample 4) will be collected (making a total of 4 samples over approximately 4 weeks) to ensure that parameters remain stable and do not go below pre-specified thresholds (see below) for discontinuation. During this monitoring, the patient may remain on study drug provided each of the following conditions are met:

- The observed values for all samples for the parameter in question remain above the following thresholds
  - 11.5/13.0 g/dL (Female/Male) for hemoglobin and at least 1 g/dL decrease from baseline
  - 2500/mm^3 for white blood cell count
  - 1250/mm^3 for neutrophils
  - 100,000 mm^3 for platelets
- There is not, in sample 2, 3, or 4 a further decrease relative to sample 1 in the measure being monitored
  - > 2 g/dL if the measure of interest is hemoglobin
  - > 500/mm^3 if the measure of interest is neutrophils,
  - > 1500 mm^3 if the measure of interest is white blood cell count,
  - > 50,000/mm^3 if the measure of interest is platelets.

- After samples 2, 3, and 4 have been obtained, and if no decrease relative to sample 1 meeting the criteria described in the above bullets has been observed, the patient may continue in the study on the usual visit schedule and the AESI is considered resolved.
- In the event samples 2, 3 and 4 show a further decrease from sample 1 that exceeds the above criteria for the relevant measure, drug administration is halted. A repeat laboratory sample should be obtained within one week. Provided this repeat sample shows an increase from the value among sample 2, 3 or 4 that triggered the halt, study drug may be reinstated, with weekly monitoring of the relevant parameter for at least 2 samples to ensure that values remain above 100,000/ $\mu$ L for platelets, 1250/mm^3 for neutrophils and 2500/mm^3 for WBCs.

Confirmed Events of Special Interest are recorded in the EDC system by completing the AE form electronically and indicating the event as an AE of Special Interest. Since these protocol defined AESIs are intended for safety monitoring, they may not be considered untoward medical events and their monitoring should not be used to infer relationship to drug.

When a patient is discontinued, best efforts should be made by the Investigator to complete final safety assessments and follow ongoing AEs until resolution or no longer of clinical concern.

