### 11.10.2.2 Adverse Events of Special Interest and Monitoring Procedure

The following AEs are designated as events of special interest, and, if observed as treatment-emergent during the study, should be addressed as described below: Anemia, leukopenia, neutropenia, thrombocytopenia, renal impairment, congestive heart failure, suicidality.

Observation	Risk Management
Clinical Laboratory Parameters for Adverse Events of Special Interest	
Cardiac Conduction: QTcF $\geq$ 500 ms or QTcF increase from baseline $\geq$ 60 ms and QTcF $\geq$ 480 ms	
 
For any observed case, the investigator should repeat the ECG assessment twice and compare the average of these 3 measurements of QTcF to the average of the 2 pre-treatment (i.e. screening and baseline) QTcF values
 
If confirmed, patient should be discontinued and appropriate follow-up instituted
 

Anemia: Hemoglobin decrease from baseline $> 2$ g/dL, or a decrease from baseline of at least 1.0 g/dL to a value below 11.5 g/dL (female) or 13 g/dL (male)	
 
For any observed case, repeat laboratory test within one week to confirm: 
 
If the abnormality persists on repeat laboratory test, refer to section 11.10.2.2.1 for additional laboratory monitoring and initiate appropriate medical work-up to assess potential causes.
 
 
 

Leukopenia: White blood cell count $< 2500/\text{mm}^3$ ; or a decrease from baseline $> 1500/\text{mm}^3$	
Neutropenia: Neutrophil count $< 1250/\text{mm}^3$ ; or decrease from baseline $> 500/\text{mm}^3$	
Platelet count $< 100,000/\text{mm}^3$ ; or a decrease from baseline $> 50,000/\text{mm}^3$	
eGFR $< 30 \text{ ml/min}/1.73 \text{ m}^2$	
 
Confirm with repeat test within one week; if confirmed, patient should be discontinued and appropriate follow-up instituted
 

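### A white-cell, neutrophil or platelet count that stays below its absolute limit without a large fall triggers an AESI in Protocol 11.10.2.2 but cannot be confirmed under 11.10.2.2.1

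*Protocol*

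**What the plan says.** The table in Protocol 11.10.2.2 gives two alternative triggers for each of three counts. Exclusion criterion 17 (Section 7.3.2) sets the eligibility floor at the same absolute limits.

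| Count (/mm³) | Absolute trigger | Fall-from-baseline trigger | Lowest eligible value |
|---|---|---|---|
| White cells | < 2500 | > 1500 | 2500 |
| Neutrophils | < 1250 | > 500 | 1250 |
| Platelets | < 100,000 | > 50,000 | 100,000 |

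The test is repeated within a week. Then: "If the abnormality persists on repeat laboratory test, refer to section 11.10.2.2.1 for additional laboratory monitoring and initiate appropriate medical work-up". In the table as extracted, this instruction stands beside the anemia row and the cells beside the next three rows are empty. I read it as one merged cell covering all four blood-count rows.

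Section 11.10.2.2.1 then says:

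- Entry: "When an event is identified as meeting the pre-specified criteria for decrease from baseline in a laboratory sample".
- Confirmation: "Confirmation is defined as a repeat value that 1) meets the magnitude of decrease criterion from baseline relative to sample 1", and in addition no meaningful rise from sample 1. Baseline is the lowest count available before randomization.
- Samples 3 and 4 follow once the fall is confirmed. Their purpose is "to ensure that parameters remain stable and do not go below pre-specified thresholds (see below) for discontinuation".
- Staying on drug requires a set of conditions, all of which must hold. The first is "The observed values for all samples for the parameter in question remain above the following thresholds", with 2500, 1250 and 100,000 listed for these counts. The second is no further fall from sample 1 larger than the sizes in the table above.
- The last bullet says that, if samples 2 to 4 show no such decrease relative to sample 1, "the patient may continue in the study on the usual visit schedule and the AESI is considered resolved".
- The halt applies "In the event samples 2, 3 and 4 show a further decrease from sample 1 that exceeds the above criteria for the relevant measure".
- Recording: "Confirmed Events of Special Interest are recorded in the EDC system by completing the AE form electronically", with the event marked as an AESI.

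On the analysis side, the protocol names seven events of special interest and SAP 4.4.1 names six. The missing one is neutropenia. SAP 11.1 plans a table of all ESIs, and SAP Section 1 gives the SAP precedence over the protocol for planned analyses.

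**The concern.** The trigger has two limbs, and the section it leads to is written for one of them. A count that is low in absolute terms, in a patient who started low, can trigger the AESI and persist on repeat, and then reach a section that does not admit it. Two sites following the same text could handle the same patient differently: one through the referral, the other stopping at the definition of confirmation.

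Three things depend on the answer: whether samples 3 and 4 are drawn, whether the event is flagged as an AESI in the database, and whether the section's stay-on-drug conditions are reached at all. The ad hoc report to the Data Monitoring Committee in Section 11.10.1.2 also depends on it, because that report is prompted by discontinuation for an AESI. For QTcF and eGFR the same table states plainly that a confirmed event means discontinuation. The blood-count rows rely on the referral instead.

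The SAP omission is a separate matter. An ESI table built from the SAP list would leave neutropenia out.

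**Working it through.** There is no figure in the plan to reproduce. The check applies the written rules to possible counts. All limits come from Protocol 11.10.2.2, 11.10.2.2.1 and exclusion 17. The individual patients below are illustrations.

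**Step 1: which baselines are affected.** Let B be baseline, L the absolute limit, D the decrease criterion and v the observed count. The count triggers through the absolute limb alone if v < L and B − v ≤ D, that is, if v lies from B − D up to (but not including) L. Such a v exists when B < L + D.

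| Count (/mm³) | L + D | Eligible baselines affected |
|---|---|---|
| Neutrophils | 1250 + 500 = 1750 | 1250 to < 1750 |
| White cells | 2500 + 1500 = 4000 | 2500 to < 4000 |
| Platelets | 100,000 + 50,000 = 150,000 | 100,000 to < 150,000 |

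Taking the lowest pre-randomization value as B makes the computed fall smaller, so it makes the fall criterion harder to meet.

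**Step 2: the rules applied to examples (sample 2 equal to sample 1).**

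| Baseline → stable value | Fall | Absolute trigger met and persisting? | Fall criterion met, so entry and confirmation? | Above limit, as staying on drug requires? |
|---|---|---|---|---|
| Neutrophils 1500 → 1150 | 350 | Yes (< 1250) | No (350 ≤ 500) | No |
| Neutrophils 1300 → 900 | 400 (31%) | Yes (< 1250) | No (400 ≤ 500) | No |
| White cells 3200 → 2300 | 900 | Yes (< 2500) | No (900 ≤ 1500) | No |
| Platelets 120,000 → 95,000 | 25,000 | Yes (< 100,000) | No (25,000 ≤ 50,000) | No |

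By comparison, neutrophils going from 5000 to a stable 4400 (fall 600, or 12%) meet the fall criterion and enter the section without ambiguity, at a much higher count.

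**Step 3: what happens if the referral alone opens the section.** Take 1300 with samples 1 to 4 all at 900. The first stay-on-drug condition fails, because 900 is not above 1250. The further fall from sample 1 is 900 − 900 = 0, so the halt paragraph is not reached and the test in the last bullet is passed. That bullet would then call the AESI resolved while the count is still below a limit that the section itself labels as one for discontinuation.

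**Step 4: hemoglobin.** Both hemoglobin triggers already contain a fall. A man going from 13.2 to 12.8 g/dL (fall 0.4) triggers neither. The mismatch is confined to white cells, neutrophils and platelets.

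**The case against.** The strongest reply is that the drug decision is already settled. The stay-on-drug conditions are cumulative, the absolute limits are described as discontinuation thresholds, and the last bullet sits in the same list and cannot revive a condition that has failed. It also speaks of continuing in the study, whereas the list is about remaining on study drug. A reader might infer from Step 3 that the protocol gives contradictory instructions on whether a patient below the limit may stay on drug. The text does not support that: once the section applies, the patient may not. What remains out of line is the statement that the AESI is resolved.

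Second, the referral in 11.10.2.2 is not limited to falls and already requires a repeat and a medical work-up. That is true, and a loose reading of the entry sentence could let these patients in. The definition of confirmation is explicit, however, and still fails for them.

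Third, the reach of the referral to the three lower rows is inferred from the table layout. It is an inference, but a sound one, because 11.10.2.2.1 lists thresholds for exactly those counts.

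Fourth, a reader might quote the extreme white-cell case: baseline 2500 and a count of 2500 − 1500 = 1000 with no qualifying fall. That overstates the size. At a count of 1000, avoiding the neutrophil fall criterion needs neutrophils of at least 1250 − 500 = 750, which leaves at most 250 for lymphocytes. Otherwise the patient enters through neutrophils.

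Fifth, there are other safeguards: discontinuation for a severe laboratory abnormality or on investigator judgment (7.7), roughly weekly follow-up of clinically significant findings (11.4), and central-laboratory alerts (11.10.1.1). They reduce the harm, but they do not say whether the event counts as confirmed.

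On the SAP, neutropenia recorded as an adverse event would still appear in the general treatment-emergent tables, and Protocol 10.3.7 plans a table of special-interest laboratory findings. The omission affects the ESI table, not all reporting of neutropenia.

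**Conclusion.** The concern holds as a mismatch between a two-limb trigger and a one-limb confirmation rule. In the baseline ranges of Step 1, a white-cell, neutrophil or platelet count can remain below its absolute limit without meeting the definition of a confirmed AESI, so samples 3 and 4 and the AESI flag do not literally apply. Where the section is applied through the referral, only its last bullet gives a wrong result.

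This rests on the printed limits and on reading the risk-management cell as merged. The number of affected patients cannot be estimated, because the documents give neither a distribution of baseline counts nor a rate of values below the limits. Severity is minor to moderate: a stated confirmation rule and a governing ESI list give wrong results if followed as written, but existing safeguards limit the consequences.

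A reader might also conclude that a new mandatory stop is needed. The documents do not call for one. A stable move from 1300 to 1240, a fall of 60, shows why a further stop with no restart route would be open to debate.

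**What to change.** 1. In Protocol 11.10.2.2.1, open the section to any white-cell, neutrophil or platelet criterion in 11.10.2.2. Define confirmation as a repeat that again meets either the absolute or the decrease criterion, without a meaningful increase from sample 1.
2. Amend the last bullet so that the AESI is resolved, and the patient continues, only if the first condition (all samples above the absolute limits) is also met. Keep all thresholds and leave the halt and restart paragraph unchanged. Add no new stop or restart rule.
3. Separately, add neutropenia to the ESI list in SAP 4.4.1, so that it appears in the ESI table of SAP 11.1.

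The cost is a short protocol amendment, one word in the SAP and a few extra blood counts. Item 1 does make the section's existing first condition apply beyond doubt to these low-baseline patients, and the sponsor should confirm that this is intended.

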22. Participation within 1 month of Screening in a clinical trial involving treatment with an investigational product. Concurrent participation in an observational study (ie, no investigational treatment being used) is allowed provided it does not interfere with the procedures and conduct of this protocol.
23. Any serious medical condition or comorbidity, laboratory abnormality, or psychiatric illness not otherwise specified that could place the patient at undue risk during trial participation, that could confound the results of the study, or that could reasonably be expected to affect patient compliance with study requirements for treatment and evaluation, as judged by the Investigator.
24. Any known recent exposure within the 14 days prior to initial Screening to COVID-19 or symptoms of COVID-19 infection or other reason to suspect COVID-19 infection as assessed by the Investigator at the time of initial Screening.

Note: Abnormal Screening laboratory values that appear to be spurious (eg, laboratory error), or that are the result of an identified transient event that if resolved is unlikely to recur, may be repeated once. Should this occur, the Investigator should document the reason for repeating the test, and if the repeat examination is within the acceptable range, the patient may participate.

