#### 4.4.2. *Laboratory safety assessments*

The laboratory tests that will be collected at the timepoints specified are presented in the schedule of events (Exhibit 3). Abnormal Screening laboratory values that appear to be spurious, or that are the result of a transient event, may be repeated once; in this circumstance the repeated value will be utilized as the value of record for analysis purposes.

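### Protocol 11.10.2.2.1 does not exclude a spurious, superseded Screening haemoglobin from its lowest-value baseline, so in the few (possibly no) patients admitted on such a repeat, anaemia cannot be confirmed as an event of special interest until haemoglobin is 1.0 g/dL below the rejected value

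*Protocol*

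**What the plan says.** **Entry.** The note closing Protocol 7.3.2 covers an abnormal Screening value that looks like laboratory error, or that is "the result of an identified transient event that if resolved is unlikely to recur, may be repeated once". The reason must be documented, and "if the repeat examination is within the acceptable range, the patient may participate". Exclusion criterion 17 puts the haemoglobin limit at 11.5 g/dL for women and 13 g/dL for men.

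**Trigger.** The anaemia row of the table in Protocol 11.10.2.2 begins "Anemia: Hemoglobin decrease from baseline". It asks for a fall of more than 2 g/dL, or a fall of at least 1.0 g/dL ending below 11.5 (women) or 13 (men). Both limbs need a fall from baseline, and the table does not say which value baseline is. White cells, neutrophils and platelets each also have a stand-alone absolute limit. A low result is repeated within a week: "If the abnormality persists on repeat laboratory test, refer to section 11.10.2.2.1 for additional laboratory monitoring", together with a medical work-up.

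**Confirmation.** Protocol 11.10.2.2.1 states: "Confirmation is defined as a repeat value that 1) meets the magnitude of decrease criterion from baseline relative to sample 1", and adds that the repeat must not show a meaningful rise from sample 1. Then: "Baseline for this purpose is defined as the lowest of the available pre-randomization values". The consequences follow from confirmation: "If the decrease is confirmed, additional weekly samples for the ensuing 2 weeks" are collected as samples 3 and 4, conditions for staying on study drug apply during that monitoring, and confirmed events are entered with the special-interest mark.

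**Superseded values.** SAP 4.4.2 addresses a repeated Screening test: "in this circumstance the repeated value will be utilized as the value of record for analysis purposes". For assessments other than the NRS, SAP 6.1.3 takes baseline as the last value before randomization and first dose.

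**The concern.** A patient admitted on a repeated haemoglobin has, by construction, a first result below the entry limit on file. For eligibility the protocol sets that result aside. For safety confirmation nothing sets it aside, so unless Day 1 is at or below it, the rejected result is the lowest and becomes the reference. The only text that replaces it is SAP 4.4.2, which is confined to analysis and gives no instruction to a site applying 11.10.2.2.1.

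Haemoglobin is the parameter most exposed, because it has no absolute trigger to fall back on. Followed to the letter, the rule measures a fall on treatment from a number already documented as wrong. At stake are the special-interest flag, the two automatic weekly samples, and the stay-on-drug check that goes with them.

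**Working it through.** The documents state no figure for this rule, so the check applies the rule to assumed haemoglobin values on a 0.1 g/dL grid.

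**Inputs.** L = entry limit (13 men, 11.5 women; Protocol 7.3.2). R = rejected Screening value, below L. A = lowest accepted pre-randomization value, at or above L. Day 1 is above R. I read the first limb of confirmation as requiring sample 2 to meet the fall from baseline again.

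**Criterion** (Protocol 11.10.2.2). A value v meets it against baseline B if B − v > 2, or if B − v ≥ 1.0 and v < L.

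**Baseline R, as written.** R is below L, so the second limb governs: met at v ≤ R − 1.0. As R is at most 12.9 (men) or 11.4 (women), confirmation never occurs above 11.9 or 10.4.

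**Baseline A, rejected value left out.** Met at v ≤ min(A − 1.0, L − 0.1), for A up to 15.0 (men) or 13.5 (women). Above those, the limb of more than 2 g/dL takes over.

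**Unconfirmed band.** From R − 0.9 up to min(A − 1.0, L − 0.1).

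| Sex | R | A | Confirmed at, R counted | Confirmed at, R left out | Unconfirmed | Fall from A |
|---|---|---|---|---|---|---|
| M | 12.9 | 13.0 | ≤ 11.9 | ≤ 12.0 | 12.0 only | 1.0 |
| M | 12.4 | 13.4 | ≤ 11.4 | ≤ 12.4 | 11.5–12.4 | 1.0–1.9 |
| M | 12.4 | 14.5 | ≤ 11.4 | ≤ 12.9 | 11.5–12.9 | 1.6–3.0 |
| M | 9.0 | 14.0 | ≤ 8.0 | ≤ 12.9 | 8.1–12.9 | 1.1–5.9 |
| F | 11.4 | 11.5 | ≤ 10.4 | ≤ 10.5 | 10.5 only | 1.0 |
| F | 11.0 | 12.5 | ≤ 10.0 | ≤ 11.4 | 10.1–11.4 | 1.1–2.4 |

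The fourth row shows a gross laboratory error; the rule puts no floor under such a value.

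**Is the fall flagged at all?** That depends on the baseline in the 11.10.2.2 table.
- If it is Day 1, the first low result triggers the repeat and, if the abnormality persists, the work-up, but confirmation can still fail. The QTcF row, which names screening and baseline as separate values, and SAP 6.1.3 lean this way.
- If the definition in 11.10.2.2.1 also governs sample 1, a value in the band is not flagged under the special-interest rule at all. That paragraph covers both identification and confirmation, so this reading is open.

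**Samples 3 and 4.** Haematology is scheduled at Weeks 1, 2, 4, 8, 12, 14, 18, 24 and 28 (SAP Exhibit 3). With sample 2 assumed one week after sample 1, samples 3 and 4 fall two and three weeks after it.
- First low value at Week 4, 8, 14 or 18: no scheduled draw replaces either sample. The next scheduled draw comes 4, 4, 4 or 6 weeks after sample 1.
- At Week 1, 2 or 12: one scheduled draw (Week 4, 4 or 14) replaces one of them.
- At Week 24 dosing has ended.

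This counts scheduled draws only. Under Protocol 11.4 the investigator follows a patient about weekly if the finding is considered clinically significant against the randomization value. The gap therefore appears in full only where that step is not taken.

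**The case against.** **Little is at stake.** Harm needs a chain: a low first haemoglobin, an in-range repeat, Day 1 above the rejected value, a later fall inside the band, persistence, and no weekly follow-up under Protocol 11.4. Two of the six assumed pairs give a band of a single value. This stands and fixes the severity. It does not make the rule right, because 11.4 depends on the investigator's opinion whereas samples 3 and 4 are automatic.

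**The sponsor chose the lowest value on purpose.** A lowest-value reference guards against over-calling, and 11.10.2.2.1 itself says these events are monitoring tools that may not be untoward. For a resolved transient event this stands: the low was a real level off active drug, and the sponsor may wish to keep it. A reader might infer that every superseded value must be excluded; the documents do not require that. The argument does not reach a spurious result, which was never the patient's level. One could read the word available as meaning available and valid, but the text does not say so.

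**The gap exists without any repeat.** True. With Screening 13.2 and Day 1 14.2, a man meets the criterion against Day 1 at 12.9 or below and against the lowest value at 12.2 or below. That gap lies between two valid, in-range values and is the sponsor's choice. It also means the fix is partial: with 12.0 rejected, repeat 13.5 and Day 1 13.8, confirmation moves from 11.0 to 12.5, still short of 12.8 against Day 1.

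**The SAP is applied unevenly.** One may object that SAP 4.4.2 is denied reach over site monitoring while SAP 6.1.3 is used to interpret the trigger table. The point does not need SAP 6.1.3: confirmation fails under either reading of the table.

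**Conclusion.** The rule gives a wrong result for a Screening haemoglobin documented as spurious and replaced by an acceptable repeat. With Day 1 above the rejected value, anaemia is not confirmed as an event of special interest until haemoglobin is at least 1.0 g/dL below that value. Depending on which baseline the trigger table uses, a fall in the band is either detected and left unconfirmed, or not flagged under this rule at all.

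A reader might infer that anaemia would be missed. The documents do not support that. Scheduled haematology, ordinary adverse event recording (Protocol 11.1.2), central-laboratory alerts (11.10.1.1), the laboratory tables (10.3.7) and follow-up under 11.4 do not depend on confirmation. What is lost is the flag, the automatic samples and the stay-on-drug check. No efficacy inference is touched.

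The haemoglobin pairs are assumptions, and the number of patients admitted on such a repeat is not given; it is probably small and may be zero. Severity: minor.

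**What to change.** In Protocol 11.10.2.2.1, after the baseline definition, add: *not counting a Screening result documented as spurious and superseded by an acceptable repeat*. Mark such results in the central-laboratory alert so that sites apply the same reference.

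If the triggers in 11.10.2.2 share this baseline, apply the same exclusion there. If they use Day 1, leave them alone: imposing the lowest value would make them less sensitive.

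Extending the clause to resolved transient-event values would match SAP 4.4.2, but that is for the sponsor to decide. The separate gap between Day 1 and the lowest valid value stays as the sponsor set it. No threshold changes.

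The cost is one clause and one laboratory flag, with a few more confirmatory samples and possibly an earlier stop of study drug in such a patient under the existing rule. A change to a safety rule needs sponsor, investigator and IRB approval (Protocol 12.5) at about 50 sites, so it is best added at the next amendment.

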### 11.1.2 Documenting and Reporting Adverse Events

The Investigator is responsible for routine assessments of AEs throughout the course of the study. All clinical complaints, symptoms, or signs that meet the AE definition will be documented in the patient’s record and entered in the study database. Source documentation

should be maintained that allows for clear identification of each AE and the following parameters:

- Date of onset
- Date of resolution (or indication that the event continues as of the final visit)
- Intensity (mild, moderate, severe)
- Seriousness (per SAE definition)
- Relationship to study treatment
- Outcome

For study data collection purposes, the outcome of AEs captured in the database will be reviewed and made final at the time of the final study evaluation for each patient. If the AE is ongoing, this will be reflected in the record. However, the study Investigator is responsible for following all AEs until resolution or until no longer of clinical concern.

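### A haematological AESI triggered by a fall from baseline is declared resolved by comparison with sample 1, so a value that still meets the AESI criterion can be labelled resolved (minor)

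*Protocol*

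**What the plan says.** Protocol 11.10.2.2 sets the haematological triggers. Each parameter has a fall-from-baseline criterion and an absolute low-value criterion. An observed case is repeated within a week, and a persisting abnormality leads to medical work-up and the monitoring in 11.10.2.2.1.

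In 11.10.2.2.1 the reference for the fall is explicit: "Baseline for this purpose is defined as the lowest of the available pre-randomization values". Sample 2 confirms the event if it still meets the fall-from-baseline criterion and has not risen meaningfully from sample 1. Two further weekly samples follow, "making a total of 4 samples over approximately 4 weeks". Their purpose is "to ensure that parameters remain stable and do not go below pre-specified thresholds".

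The closing rule changes the reference. After samples 2, 3 and 4, "if no decrease relative to sample 1 meeting the criteria described in the above bullets has been observed", then "the patient may continue in the study on the usual visit schedule and the AESI is considered resolved".

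The same section adds that "Confirmed Events of Special Interest are recorded in the EDC system by completing the AE form electronically". Protocol 11.1.2 requires each AE record to carry either a resolution date or a flag that the event is still continuing. It also makes the investigator responsible for following AEs until they resolve or cease to be a clinical concern.

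**The concern.** The event opens on one reference (baseline) and closes on another (sample 1). The pattern that confirms it at sample 2, low and not rising, is the same pattern that closes it when repeated at samples 3 and 4. Stability above a floor is a good reason to stop extra blood draws. It is not evidence that the count has recovered.

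Two things are at stake. A site that takes the clause at face value could enter a resolution date on the AE form for a fall that persists. And the follow-up that the protocol ties to unresolved events (11.1.2, and the unresolved-TEAE route in 11.4) could be treated as complete.

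**Working it through.** The plan states no figure to reproduce. The check applies the decision rule to the protocol's own limits.

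**Inputs.** T is the fall-from-baseline trigger (11.10.2.2). The further-fall limit against sample 1 (11.10.2.2.1) has the same size. F is the absolute floor (11.10.2.2.1). B is baseline and S1 to S4 are the samples.

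**Rule.** I read the closing clause together with the floors, which is the reading kinder to the plan. The event is called resolved if all samples exceed F and S1 − Sk ≤ T for k = 2, 3, 4. It still meets the AESI criterion if B − Sk > T.

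**Flat fall just past the trigger.** S1 is just below B − T and must exceed F, so B > F + T.

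**Fall deepening to about twice the trigger.** The largest later fall is (B − S1) + T, which is about 2T when S1 is just past the trigger. The value must also stay above F, so B > F + 2T.

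| Parameter | T | F | F + T | F + 2T |
|---|---|---|---|---|
| Haemoglobin, men (g/dL) | 2 | 13.0 | 15.0 | 17.0 |
| Haemoglobin, women (g/dL) | 2 | 11.5 | 13.5 | 15.5 |
| White cells (/mm3) | 1500 | 2500 | 4000 | 5500 |
| Neutrophils (/mm3) | 500 | 1250 | 1750 | 2250 |
| Platelets (/mm3) | 50,000 | 100,000 | 150,000 | 200,000 |

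**Illustrations (baselines are my assumptions).**
- Platelets 220,000, then 169,000 four times: no further fall, above the floor, called resolved. The fall is 51,000 (51/220 = 23%), still over 50,000.
- Neutrophils 4000, then 3490, 3490, 3200, 3000: S1 − S4 = 490, within 500, called resolved. The fall is 1000 (25%), twice the trigger.
- Platelets 250,000, then 199,000, 199,000, 175,000, 150,000: S1 − S4 = 49,000, within 50,000, called resolved. The fall is 100,000 (40%).
- Haemoglobin in a man with baseline 16.0: S1 = 13.9, and the floor stops the fall at 13.1. That is 2.9 g/dL, or 1.45 times the trigger.

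**Time to the next scheduled haematology.** Nominal days are 7, 14, 28, 56, 84, 98, 126, 168 and 196. Sample 2 may be drawn at any time within a week of sample 1 and samples 3 and 4 follow weekly. For a repeat drawn 1 to 7 days later, sample 4 therefore falls 15 to 21 days after sample 1, or 28 days after it if the four-week description is taken literally.

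| Sample 1 (day) | Wait if sample 4 at +15 | at +21 | at +28 |
|---|---|---|---|
| Week 1 (7) | 6 | 0 | 21 |
| Weeks 2, 12, 18 (14, 84, 126) | 27 | 21 | 14 |
| Weeks 4, 8, 14, 24 (28, 56, 98, 168) | 13 | 7 | 0 |

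For example, a Week 18 trigger repeated the next day puts sample 4 on day 141, and 168 − 141 = 27 days. The range is 0 to 27 days, about 0 to 4 weeks. Week 28 is the last scheduled haematology, so nothing follows a trigger there.

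**The case against.** The best defence is that the clause closes a monitoring episode and makes no statement about the count. The section is about confirmatory monitoring, and it says these AESIs serve safety monitoring and need not be adverse medical occurrences. The floors match exclusion criterion 17, so every value called resolved is one at which that parameter would have allowed entry. Stopping extra draws there is a defensible choice. That stands as a case for ending the sampling. It does not rescue the label: the sentence separately returns the patient to the usual schedule and declares the event resolved, and the same section sends the event to the AE form.

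The safeguards also stand, and they limit the harm:
- AE outcomes "will be reviewed and made final at the time of the final study evaluation for each patient" (11.1.2).
- The route in 11.4 for clinically significant laboratory findings does not depend on the AESI label.
- Work-up on confirmation, the floors and DMC review are untouched.
- A value still low at the next scheduled draw meets the trigger again and calls for a repeat within a week.
- Laboratory summaries of change from baseline (Protocol 10.3.7; SAP 11.2, which names fewer time points) use the measured values, so the fall enters them whatever the AE outcome field says.

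A reader might infer more than this: that sites are told to enter a resolution date at sample 4, that an affected patient goes unmonitored, that any patient's fall may double, or that the safety tables are biased. The documents support none of these. No section instructs the date. The safeguards above continue. Doubling needs the higher baselines. AE tables count a patient once per preferred term, and no table of AE outcome or duration is planned.

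**Conclusion.** The clause is wrong as written, and the consequence is minor. Followed exactly, it gives resolved status to values that still meet the AESI criterion. This happens for a flat fall just past the trigger at baselines above F + T, and for a fall of about twice the trigger only at baselines above F + 2T. If sample 1 is already well past the trigger, the total fall can exceed twice the trigger, still capped by the floor.

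The problem is confined to AESIs triggered by a fall from baseline. Those triggered by an absolute low value fail the condition for staying on drug. What is exposed is the recorded outcome and the follow-up tied to unresolved events, and this is a risk of misrecording, not a certainty.

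The thresholds follow directly from the protocol's limits. The 0 to 4 week wait assumes nominal visit days and the sampling spacings shown. How often this would occur cannot be estimated, because the documents give neither the baseline distribution nor the within-patient variability of these counts.

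**What to change.** In Protocol 11.10.2.2.1, replace the closing statement about resolution with *additional confirmatory monitoring ends*. Add that the AESI outcome is recorded as resolved only when the value no longer meets the 11.10.2.2 criterion against baseline, and otherwise as ongoing. State also that later scheduled values are still assessed under 11.10.2.2, including the one-week repeat. Without that sentence, an event left ongoing with its monitoring ended might be read as needing no further repeats, and sampling could fall.

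The cost is a short wording change and an EDC completion guideline. It needs no added scheduled visit and no change to a stopping threshold or planned analysis. The downside is that some events will stay coded as ongoing although values are stable above every floor, with follow-up under 11.1.2 and 11.4 left to the investigator's judgement.
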